7.6.2 BPI Short Form – Modified for CIPN

The Brief Pain Inventory (BPI) short form⁴⁴ is a pain assessment tool used with cancer patients to measure both severity of pain (first 5 items) and interference caused by pain (item 6 with 7 components) on 0-10 scales (0=does not interfere; 10=completely interferes.) It is widely used in cancer pain evaluation⁴⁵ and has been modified specifically for neuropathy⁴⁶.

The BPI short form will be completed at baseline, end of treatment and at 1 month (28 days), 2 months (8 weeks), and 3 months (12 weeks) after the Scrambler/Sham therapy. Those participating in sham therapy group and choosing Scrambler therapy after 28 days, will complete the BPI at the end of Scrambler therapy, and at 1 and 2 months after the Scrambler therapy. Before and after Scrambler/Sham therapy daily, the “pain now” question from the BPI (question #4) will be asked and documented, as in prior studies.

7.6.3 European Organization for Research and Treatment of Cancer Quality of Life Cancer Chemotherapy Induced Peripheral Neuropathy-20 Instrument (CIPN-20)

The EORTC QLQ-CIPN20⁴⁷ is a 20-item CIPN-specific questionnaire which includes three scales assessing sensory (9 items: #31-36, 39, 40, 48), motor (8 items: #37, 38, 41-45, 49), and autonomic (3 items: #46, 47, 50) symptoms and functioning with each item measured on a 1-4 scale (1 – not at all; 4 – very much). The EORTC QLQ-CIPN20 has been tested in cancer patients receiving a variety of chemotherapies and has been shown to have internal consistency reliability based on Cronbach’s alpha coefficients of 0.82, 0.73, and 0.76 for the three scales, respectively, with excellent validity and reliability⁴⁸. The CIPN-20 will be completed at baseline, end of treatment and at 1 month (28 days), 2 months (8 weeks), and 3 months (12 weeks) after the Scrambler/Sham therapy. Those participating in sham therapy group and choosing Scrambler

therapy after 28 days, will complete the CIPN-20 at the end of Scrambler therapy, and at 1 and 2 months after the Scrambler therapy.

NOTE: Please see questionnaires in Appendices A and B.

7.6.4 Concomitant Medications

Participants will also keep a diary where they will record each dose of pain medication (prescription and over the counter) they take in real time throughout each 24 hour period during Scrambler/sham intervention. This diary will be brought to the sessions and the study coordinator (**NOT the study team member administering the intervention**) will review the diary for completeness and clarity. Participants will also be asked to complete a diary of pain medications for a 7-day period around the time of the monthly follow-up timepoints as outlined above for the patient-reported outcomes.

The following table will be used to convert all opiates to morphine oral dose equivalents (MOEDs), when applicable:

Morphine oral dose equivalents ⁴⁹					
Drug intake for prior 24 hours	Oral Equivalent	Parental equivalent	Doses and Total mgs taken	Conversion Factor	Total MOED (mg)
Morphine immediate release	30 mg	10 mg			
Morphine sustained release	30	10			
Codeine	200 mg	100 mg			
Oxycodone immediate release	20 mg	Not available			
Oxycodone extended release	20 mg	Not available			
Hydrocodone immediate release	30 mg	Not available			
Hydromorphone	7.5 mg	1.5 mg			
Methadone	10 mg	5 mg			
Fentanyl transdermal	1 mcg/hour equivalent to 2 mg oral morphine/hour				
TOTAL					

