3.2 Secondary

3.2.1 The secondary endpoints will include changes in the complete Brief Pain Inventory, the CIPN EORTC Q-20 scale, and changes in pain drug use.

3.2.2 The primary measurement tools used to determine if MC-5A Calmare therapy will improve endpoints include the following: neuropathy (European Organization for Research and Treatment of Cancer Quality of Life Cancer Chemotherapy Induced Peripheral Neuropathy-20 Instrument (CIPN-20)); opiate use (morphine oral equivalent daily dose, MOED) and other drug (anti-depressant, anti-convulsant) use. We will also study the duration of the effect.

4. Hypotheses

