4.2 Secondary

- Scrambler Therapy will result in significant improvements in the total CIPN modified Brief Pain Inventory score and the motor and sensory subscales of the CIPN 20 compared to sham therapy.
- Pain medication and morphine oral equivalent dose (MOED) daily amounts will decrease by at least 20% more from the start of treatment Day 1 (pre) to Day 30 days (post), in the group receiving scrambler therapy versus those who received sham therapy.

5. Background and Rationale

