13.1 Overall

The primary endpoint is change in patient-reported pain from day 0 to day 28 as measured by the Modified Brief Pain Index, question #3 (Appendix B). This endpoint also serves to get preliminary information for planning future, larger, phase III studies.

Secondary endpoints will include the total Brief Pain Inventory score, the sensory and motor subscales of the CIPN 20, and the Morphine Oral Equivalents Dose at day 28 compared to sham therapy. We will also report the daily (days 1-10) changes in “pain now” before and after each treatment, to be comparable to all the other reported studies.

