13.2 Sample Size and Accrual

We are anticipating that the starting pain score will be 4-6 based on VCU, Italian, and Mayo Clinic data. We are anticipating that the reduction in CIPN pain score will be over 50% based on the VCU, Italian, and Mayo Clinic data. We anticipate a possible 10% reduction in pain scores over 30 days based on the randomized trial data for placebo compared to gabapentin and other drugs.

The primary objective of this study is to determine if patients randomized to the Scrambler therapy have a larger reduction in pain scores than those randomized to the placebo, or sham, treatment. Power calculations were performed using a simulation approach. Pain scores were simulated using a bivariate normal distribution with a mean (SD) of 4 (2) at baseline for both groups, with means ranging from 2.8 to 3.6 (30% to 10% decrease) for the control group post-treatment and mean of 2 (50% decrease) for the Scrambler group post-treatment. Post-treatment scores for both treatment arms were assumed to have a SD = 1.5. Based on previous data, a value of 0.3 was assumed for the within-patient correlation between pre- and post-treatment scores.

Any patient with 1) a simulated pain score at baseline less than 4, or 2) a simulated pain score less than 0 post-treatment, or 3) a simulated pain score greater than 10 at either time point, was replaced until all criteria were met, to reflect the actual scores we will see. Simulated scores were then rounded to the nearest integer to also reflect the nature of the scale. The change in pain score was calculated for each patient, and differences were compared between groups with a two-sample t test. Power was defined as the proportion of simulations that yielded a one-sided p value for the t test < 0.10 . 1000 simulations for each scenario were performed. The table below shows sample sizes and resulting power for the differences between treatment arms.

Total N	Power	Percent Decrease in Treatment Arm	Percent Decrease in Control Arm
30	87.3%	50%	10%
60	86.6%	50%	20%
90	77.6%	50%	30%

To detect the proposed effect size, 30 patients total, 15 on Scrambler therapy and 15 on the sham arm, will yield 87.3% power with a 1-sided type I error rate of 10%.

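### The transdermal fentanyl row of the opioid conversion table is given per hour while the table totals 24 hours, so a patch user's daily morphine equivalent can be entered at two values that differ 24-fold

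*Combined protocol and SAP*

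**What the plan says.** Section 7.6.4 introduces the table as binding: "The following table will be used to convert all opiates to morphine oral dose equivalents (MOEDs), when applicable". The first column is headed "Drug intake for prior 24 hours", the last column is a total MOED in mg, and a final row sums over drugs. The other opioid rows give oral and, where available, parenteral amounts in mg that are equivalent to one another. The transdermal fentanyl row instead reads "1 mcg/hour equivalent to 2 mg oral morphine/hour".

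The result is used in three places:
- Section 3.2 lists "opiate use (morphine oral equivalent daily dose, MOED") among the secondary measures, so the quantity is a daily dose.
- Section 4.2 sets a hypothesis on it: pain medication and MOED "daily amounts will decrease by at least 20% more from the start of treatment" in the Scrambler group than in the sham group.
- Section 13.1 names as a secondary endpoint "the Morphine Oral Equivalents Dose at day 28 compared to sham therapy".

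Section 13.3.2 allows t tests, Wilcoxon rank sum tests or Fisher's exact tests for secondary endpoints without fixing which applies to MOED. It also asks for descriptive statistics and confidence intervals, and treats all secondary p values as descriptive. Section 7.7 permits necessary concomitant medication if it is documented, so patch users can be enrolled.

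**The concern.** For every other drug, the mg taken in 24 hours times the row's ratio gives mg of morphine per 24 hours, and the results can be added. The fentanyl row starts from a delivery rate and ends in a morphine rate per hour. Before it can join the total, someone must either multiply by 24 or decide that the 2 mg is already a daily figure. The form tells the coordinator to do neither, so two people could convert the same diary to totals that differ 24-fold.

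With 15 patients per arm, one such entry can move an arm mean a long way. MOED is a named secondary endpoint with a numerical threshold attached, so the ambiguity affects a result that the trial intends to report.

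**Working it through.** **Stated design figure.** The plan gives no power or sample size for MOED. The arm size, with a one-sided error rate of 10%, comes from section 13.2: "30 patients total, 15 on Scrambler therapy and 15 on the sham arm, will yield 87.3% power with a 1-sided type I error rate of" (the quotation stops before the rate). That calculation concerns pain scores: "Pain scores were simulated using a bivariate normal distribution with a mean (SD) of 4 (2) at baseline for both groups". Repeating the simulation as described, with 10,000 runs, gives 85.6% power against the stated 87.3% for N = 30. It gives 88.0% against 86.6% for N = 60, and 75.8% against 77.6% for N = 90. The stated figures are reproduced to within 2 percentage points. MOED plays no part in them.

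**Daily value per 1 mcg/hour.**
- Literal reading: 2 mg/hour × 24 hours = 48 mg.
- The 2 mg taken on the 24-hour basis: 2 mg.
- Ratio: 48 / 2 = 24, whatever the patch strength.

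**One patch user in a 15-patient arm.** The strengths are assumptions, because the documents give none.

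| Assumed strength (mcg/hour) | Literal, mg/day | 24-hour basis, mg/day | Added to arm mean, literal | Added to arm mean, 24-hour basis |
|---|---|---|---|---|
| 12 | 576 | 24 | 38.4 | 1.6 |
| 25 | 1,200 | 50 | 80.0 | 3.3 |
| 50 | 2,400 | 100 | 160.0 | 6.7 |
| 100 | 4,800 | 200 | 320.0 | 13.3 |

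The last two columns are the daily value divided by 15.

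**Share of the arm's total.** Take one user at 25 mcg/hour and 14 others averaging 30 mg/day (assumed), so that the others total 14 × 30 = 420 mg. The patch user supplies 1,200 / 1,620 = 74% on the literal reading or 50 / 470 = 11% on the other. If the others average 10 mg/day the shares are 90% and 26%; if 60 mg/day, 59% and 6%.

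**Effect on a 20% threshold.** Use the same 15 patients as the Scrambler arm, assume no change in the sham arm, and take percent change on the arm mean in percentage points. The plan does not say how the percentage is formed, so this too is an assumption.
- The patch user stops and nobody else changes: the mean falls 1,200 / 1,620 = 74%, or 50 / 470 = 11%.
- The patch stays constant and the other 14 halve their dose: the mean falls 210 / 1,620 = 13%, or 210 / 470 = 45%.

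In both cases the two readings fall on opposite sides of 20%.

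**Effect on the tests.** An illustrative simulation (4,000 runs) had no true effect, gamma-distributed doses with mean 30 mg for the other patients, and one 25 mcg/hour user in the sham arm. The average difference in means (sham minus Scrambler) was 77.9 mg on the literal reading and 1.2 mg on the other. Simple arithmetic agrees: (1,200 − 30) / 15 = 78.0 and (50 − 30) / 15 = 1.3. The median t statistic was about 1.0 in absolute value on the literal reading and 0.1 on the other, because the extreme value also inflates the standard deviation. The mean Wilcoxon p value was 0.51 on both.

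**The case against.** The strongest reply is that a rate per hour and a 24-hour total do not contradict each other: one multiplies by 24. Read literally, the row has one meaning, and only the alternative requires treating the printed per-hour unit as a slip. The other rows carry no time base either, and the worksheet prints no conversion factor for any drug, so a missing factor is not special to fentanyl. This stands as far as it goes. The literal reading is dimensionally coherent, and nothing in the documents shows it to be an error.

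A reader might go further and infer that the row is a misprint because the literal result looks large. By the table's own oxycodone row (20 mg to 30 mg morphine), an assumed 25 mcg/hour patch corresponds to 1,200 × 20 / 30 = 800 mg of oral oxycodone a day, against 50 × 20 / 30 = 33 mg on the other reading. The documents give no benchmark for judging either figure, so they cannot show which was meant.

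It is also fair that much of the MOED assessment concerns change. A constant patch contributes zero to mg change on either reading, and the percent change of a patient who uses only fentanyl is the same on both. The Wilcoxon test, already permitted, is almost unaffected, and the p values are descriptive.

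What survives is that fentanyl alone needs a time step that no other row needs, the form does not state it, and no other section supplies it. A rank test leaves means and confidence intervals exposed.

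**Conclusion.** The point holds as an unresolved time base in one row of a binding conversion table. The factor of 24 is exact. Its effect on results is conditional: one patch user, at an assumed 12 to 100 mcg/hour, adds 38 to 320 mg or 1.6 to 13.3 mg to the mean daily MOED of a 15-patient arm.

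Exposed are the day-28 MOED level, pooled mg changes when a patch dose changes, and percent changes that mix fentanyl with other opioids. The primary endpoint, the sample size and the stated power are not exposed.

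A reader might infer that a patch user will dominate the MOED endpoint. The documents do not support that. They report no patch users, strengths or MOED distribution, and with no patch user the effect is nil. In the illustration, the literal reading distorted the estimate far more than it produced significance. The matter is worth correcting because it sets the value of a named secondary endpoint, but it does not threaten the trial's main conclusion.

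**What to change.** Check the fentanyl row against the source that the table cites, reconcile it with the 24-hour basis, and restate it explicitly in mg of oral morphine per 24 hours for each mcg/hour. Do this before any MOED is computed. Section 9 reports that 14 patients have already received treatment on the study, so recheck any MOED already converted for a patch user.

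Optionally, name the Wilcoxon test as the MOED comparison in section 13.3.2. That protects the p value but not the means or intervals, so it does not replace correcting the row.

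The cost is one table row, a check of any affected records and, if wanted, one sentence in the analysis plan. Sample size, visits and the primary analysis do not change.

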7.7 Concomitant and Supportive Therapy

The concomitant medications and therapies deemed necessary for the supportive care and safety of the subject are allowed, provided their use is documented in the medical records.

The use of other concurrent investigational drugs or devices for management of pain is not allowed unless approved by the Principal Investigator.

7.8 Discontinuation and Withdrawal of Subjects

All patients who initiate protocol intervention will be included in the overall evaluation of response (intent-to-treat analysis). All reasons for discontinuation of therapy should be documented clearly in the record.

Unless the subject refuses, follow-up will continue for the planned 12 weeks duration after the study intervention.

7.8.1 Discontinuation of Intervention

The reasons for discontinuation or protocol treatment include:

- Non-compliance with the study protocol; including, but not limited to not attending the majority of scheduled visits.
- Unacceptable major toxicity.
- Intercurrent illness or condition that would, in the judgment of the treating investigator, affect assessment of clinical status to a significant degree or require discontinuation of study intervention.
- At subject's own request. Note: The reason for discontinuation from the study must be documented. The patients will be included in the overall evaluation of response (intent-to-treat analysis) if any protocol intervention was administered prior to withdrawal.
- Study is closed or cancelled for any reason.

7.8.2 Withdrawal from Study

The reasons for withdrawal from the study include:

- Subject withdraws consent for follow-up.
- Subject is lost to follow-up.
- Study is terminated for any reason.

7.9 Additional Information

There will be co-investigators who require training on the MC5-A Calmare equipment in order to administer the scrambler and sham therapy. In order to best complete this training, it is not realistic to expect that these patients will stay blinded to the treatment assignment of the "scrambler" vs. "sham" treatment due to the communication between the staff performing the training.

The patients to be approached to take part in training will have a diagnosis also of peripheral neuropathy, as this will be the population in the randomized study. We will use the same, IRB-approved informed consent and the study team will explain to these patients that their participation will not be randomized, that they will receive scrambler therapy; however, that all other aspects of the study (including questionnaires, pain and medication diary collection) will continue as per the primary trial. This discussion will be documented in the medical and research records.

We expect to need 2-3 participants for training activities; however, in case of study staff changes during the study or any need for additional training, we will increase our recruitment goal by a total of 5 participants.

In case of any non-evaluable patients, we will increase our recruitment goal by a total of 5 participants. The total recruitment goal with all potential additional participants will be 40.

8. Study Calendar

Tests and procedures	Baseline		Daily during intervention	Follow-up ^{8,9}
	Prior to registration	Day 1 prior to first session		
Palliative care consult ¹	X			
Physical assessment ²		X	X	
Brief Pain Inventory “pain now”, before and after treatment			X	
Brief Pain Inventory Short Form-CIPN (Appendix B)		X		X
EORTC QLQ CIPN-20 scale (Appendix C)		X		X
Concomitant Medication Review (Appendix D) ³		X	X	X
Randomization ⁴		X		
Intervention: Scrambler Therapy/ Sham Treatment ^{5,6}			X	X
Patient preference ⁷		X		X

1. A palliative care consult will be required of all potential patients. This is needed to confirm medical history, current symptoms, and eligibility/appropriateness for the clinical trial. A member of the Palliative Care team at Johns Hopkins, who is also a study team member, will conduct this visit.
2. Prior to each Scrambler Therapy/Sham Treatment session a physical assessment will be done by a member of the study team to document any new/changes in physical symptoms related to CIPN; a full physical exam is not planned. This is to ensure good performance status, absence of sores, etc.
3. All pain medications will be recorded daily during intervention and for a 7 day period around follow-up questionnaires; opioids will be converted as described for data analyses.
4. Eligible subjects are randomized to receive Scrambler Therapy or Sham Treatment. Up to 5 additional participants will be included in a non-randomized fashion for training sessions with study staff; these participants will not count towards the overall accrual goal. NOTE: To distinguish training participants from those involved in the randomized clinical trial, these subjects will be assigned unique/different study numbers.
5. A phone call will be made 3-7 days after the last treatment session (Scrambler Therapy or Sham Treatment) to ask about any untoward symptoms that may have happened upon withdrawal of MCA-5.
6. Participants randomized to the sham group will be offered the option to receive the Scrambler Therapy, if, at Day 28 their pain is still ≥ 4 , and not relieved to their satisfaction. These patients will be “un-blinded” and offered 10 sessions of Scrambler therapy.
7. After the first and last session of Scrambler Therapy/Sham Treatment, participants will be asked whether they think they received the Scrambler Therapy or the Sham Treatment. After the final session, participants will also be asked the following questions: “Did the treatment help you with the pain and or numbness?” (Yes/No), and “Would you want to continue the treatment if available?” (Yes/No)
8. Follow-up may occur by phone/mail, if required.
9. Patients who receive Scrambler Therapy after Sham Treatment will have follow-up assessments at the same timepoints as if originally assigned to receive Scrambler Therapy; these participants will be on study for about 4 months to complete all assessments.

Note: The schedule should be followed as closely as is realistically possible; however, the schedule may be modified due to problems such as scheduling delays or conflicts (e.g., clinic closure, poor weather conditions, vacations, etc.) with the guidance of the Principal Investigator/designee, as appropriate, and will not be reportable as a deviation unless the endpoints of the study are affected.

9. Adverse Events

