13.3 Analysis Plan

13.3.1 Primary Endpoint

Pain scores will be summarized for each treatment arm at each time point with summary statistics. The mean change in scores in each treatment arm will be described with one sample paired t tests. The primary endpoint will be evaluated by testing for differences in change in pain scores between the two treatment arms with a one-sided t test. We will conclude a significant difference between treatment arms if the p value < 0.10. This difference will be reported with a 90% confidence interval.

Because this is a small study that is looking for an unbiased signal of activity, and the first randomized sham-controlled study for Scrambler therapy, we did not want to set the bar too high for concluding a positive effect of the treatment. This is not the definitive phase 3 studies for this treatment but more like an early randomized phase 2 study. Instead, this study will contribute information that will be useful in planning larger studies of the potential benefit of Scrambler therapy. The estimates used in the power calculation were based on data collected from a large series of patients, and even if we see the same differences in our study, we are less likely to conclude a positive treatment effect with a significance level < 0.05 due to the smaller sample size. We chose a type I error threshold of 10% to account for this, so that a p-value of 0.07 or 0.08 for the primary endpoint, for example, would not yield a negative study but instead suggest that larger studies are worthy of pursuit.

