13.3.3 Intention to treat

Analysis will be done by intention to treat, not “as treated”, with full inclusion of subjects.

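### The primary t test cannot use a patient without a Day 28 score and no rule covers such patients, so the promised full-inclusion intention-to-treat analysis cannot be delivered as written

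*Combined protocol and SAP*

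**What the plan says.** **Primary test.** Sections 13.1 and 13.3.1 define the endpoint as change from day 0 to day 28 on BPI question #3. It is evaluated by "testing for differences in change in pain scores between the two treatment arms with a one-sided t test", with significance at p < 0.10.

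**Who is analysed.** Section 13.3.3 promises intention to treat "with full inclusion of subjects". Section 7.8 includes everyone who starts the intervention, and section 7.8.1 keeps patients who withdraw after receiving any of it.

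**Extra recruits.** Section 7.9 states: "In case of any non-evaluable patients, we will increase our recruitment goal by a total of 5 participants". The term non-evaluable appears only there. The same section has a separate allowance of 5 for training participants, which gives a total of 30 + 5 + 5 = 40. Section 13.4 contains the only explicit replacement rule. It covers people who consent but never start the intervention.

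**Missing scores.** No section gives a rule for a missing Day 28 score, an expected dropout rate or a missing-data sensitivity analysis. Models that can use incomplete patients (GEE or random effects) appear only under secondary endpoints, in section 13.3.2.

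**Intermediate score.** Section 7.6.2 says: "The BPI short form will be completed at baseline, end of treatment and at 1 month (28 days"), with later visits after that. The study calendar (section 8) marks the BPI short form only before the first session and at follow-up. Section 13.3.2 lists entry and months 1, 2 and 3.

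**The concern.** A t test on change needs both scores. With no stated way to supply or model the second one, patients who lack it leave the primary analysis by default. The inclusion promise is then not met, and the allowance for non-evaluable patients makes the completed sample look full.

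With 15 per arm, one or two selective losses matter. There is some reason to think loss could be related to arm or response. The person giving treatment knows the assignment (section 7.4), and section 7.5.2 reports that half of ten pilot patients could tell they had sham. Adding patients restores power, but it does not undo selective loss. An undefined label also leaves room for a judgement about who counts, made after randomisation.

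**Working it through.** **Inputs (section 13.2).** The sample is "30 patients total, 15 on Scrambler therapy and 15 on the sham arm". Scores are bivariate normal "with a mean (SD) of 4 (2) at baseline for both groups". Post-treatment means are 3.6 for sham (10% fall) and 2.0 for Scrambler (50% fall), with SD 1.5 and correlation 0.3. Patients are redrawn if baseline is below 4, the post score is below 0 or either score exceeds 10. Scores are rounded to integers. The test is a t test on change at one-sided 0.10.

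**Step 1. Reproduce the plan's figure.** The plan says this "will yield 87.3% power with a 1-sided type I error rate of 10" per cent. A simulation with 100,000 replicates gives 85.0% if scores are rounded after the range check and 85.9% if rounded before. The plan used 1000 runs, so its Monte Carlo standard error is √(0.85 × 0.15 / 1000) = 1.1 points, and 87.3% lies about 2 standard errors above 85.0%. The stated power is not in question.

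**Step 2. What the extra 5 does.** If all 5 are randomised patients, 5/35 = 14.3% could be lost and 30 completers would remain. With 30 randomised and 5 lost at random, power on completers is 79.6% (13:12) or 78.8% (15:10), against 85.0% at 15:15. The allowance therefore protects power.

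**Step 3. What selective loss does (assumed mechanism).** Take no true difference, with both arms having the same post-treatment mean. Each Scrambler patient whose change is zero or worse is missing with probability 0.5, and nobody is missing in sham. Expected loss = 15 × P(change ≤ 0) × 0.5. For a 10% fall this is 15 × 0.267 × 0.5 = 2.0. Results of the t test on completers (40,000 replicates, rounding after the range check):

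| Fall in both arms | Mean lost of 15 | Bias (points) | Type I error, Scrambler loss | Same, lost patients replaced | Type I error, same loss in sham instead |
|---|---|---|---|---|---|
| 10% | 2.0 | +0.33 | 21.9% | 23.2% | 3.6% |
| 30% | 1.0 | +0.20 | 16.8% | 17.3% | 5.3% |
| 50% | 0.4 | +0.10 | 12.8% | 13.0% | 7.5% |

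With no loss the error is 10%. If both arms lose patients by the same rule, it stays at about 10%. Rounding before the range check moves the Scrambler-loss column to 23.3%, 17.7% and 13.8%. Replacement does not reduce the error.

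**Step 4. Would a repeated-measures analysis help?** Add an end-of-treatment score with mean 3.6, SD 1.5, correlation 0.3 with baseline and 0.5, 0.7 or 0.85 with Day 28 (all assumed). Estimate the Day 28 contrast with a likelihood-type regression that keeps the incomplete patients.

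- Loss driven by the observed end-of-treatment change: completer bias of +0.21 to +0.29 falls to between 0.00 and +0.02.
- Loss driven by the unseen Day 28 change: completer bias of +0.33 falls to +0.20, +0.15 and +0.09 for the three correlations.

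The model removes the bias in the first case and only reduces it in the second.

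**The case against.** The strongest reply is that the plan never prescribes exclusion. A reader might infer from section 7.9 that up to 5 randomised patients are to be replaced and dropped. The section does not say that the 5 are randomised, replaced or excluded, and extra recruitment to protect power is compatible with analysing everyone. Sections 7.8, 7.8.1 and 13.3.3 all say that treated patients stay in. This stands: removal of randomised patients is not a stated rule. It remains the likely reading, because training participants have their own 5 and section 13.4 already leaves non-starters out of the accrual count. It is not certain, because training participants are also outside the accrual goal and yet are inside the 40.

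The reply does not rescue the primary test. Saying that patients are included does not tell the analyst what value or model to use for them.

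Loss by Day 28 may also be small. Follow-up continues after treatment stops unless the patient refuses (section 7.8), and it may be by phone or mail (section 8). Sham patients with continuing pain are offered Scrambler only after Day 28 data collection. The coordinator is kept unaware of assignment where possible (section 7.4). These points lower the likely loss but do not replace a rule for it.

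Finally, loss confined to non-improvers in one arm has no support in the documents. That also stands, so the error rates above are illustrations.

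**Conclusion.** The concern holds in this form. As written, the primary test is by default a completer analysis, and it cannot deliver the inclusion promised in sections 7.8, 7.8.1 and 13.3.3. The undefined non-evaluable allowance in section 7.9 adds to the conflict. The intention-to-treat set also needs clarifying. Section 13.4 can remove patients already randomised, because randomisation precedes the first session, while section 13.3.3 speaks of full inclusion.

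Under the assumed one-arm loss, the type I error goes from 10% to about 21–23% if both arms fall 10% and to about 13% if both fall 50%. The mirror loss in sham lowers it to about 3–4% in the 10% case. A reader might take 22% as the trial's expected error rate. The documents do not support that: they give no dropout rate and no missingness pattern, and loss that is equal across arms leaves the error at about 10%. The 5 of 35 is a recruitment ceiling and not a forecast of loss.

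**What to change.** 1. In sections 7.9 and 13.4, define non-evaluable and state that added enrolment removes no randomised patient from the analysis. Bring sections 7.8, 7.8.1 and 13.3.3 into line with that.
2. Make the primary Day 28 contrast a mixed model for repeated measures on question #3 (baseline, end of treatment, Day 28; arm by visit) in all randomised patients, with a small-sample degrees-of-freedom correction. Keep the one-sided 0.10 level, and keep the complete-case t test as a sensitivity analysis.
3. Add a missing-not-at-random sensitivity analysis, for example missing Day 28 scored as no change, or a delta shift by arm. The mixed model alone does not deal with loss that depends on the unseen score.
4. Reconcile section 7.6.2 with the study calendar and section 13.3.2, so that the end-of-treatment BPI is clearly a scheduled visit and question #3 is collected there.

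Cost: a cheap improvement. It needs wording changes, slightly more analysis, and acceptance of a model fitted to a small sample. No new instrument is needed, and no new data if the end-of-treatment BPI is collected as section 7.6.2 says.
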